5.2. Study Day

If the visit date is on or after the date of the dose of DTX401:

Study day = (visit date – date of the dose of DTX401 + 1)

If the visit date is prior the date of the dose of DTX401:

Study day = visit date - date of the dose of DTX401.

5.3. Prior and Concomitant Medication

Prior medication is defined as any medication started before the DTX401 dose date (medication start date prior to the DTX401 dose date).

Concomitant medication is defined as any medication taken on or after the DTX401 dose date (medication end date on or after the DTX401 dose date, or ongoing).

5.4. Dose-Limiting Toxicity

A DLT is defined as any AE/SAE ≥Grade 3 that is considered by the Investigator and/or Sponsor to be related to DTX401, based on the National Cancer Institute (NCI) Common Terminology Criteria for Adverse Events (CTCAE), the most recent version.

6. ANALYSIS POPULATIONS

6.1. Full Analysis Set

The full analysis set will consist of all enrolled subjects who received DTX401. The full analysis set will be used for all the analyses.

7. DATA SCREENING AND ACCEPTANCE

7.1. General Principles

Data will be reviewed periodically, and any questionable data will be reported to the data manager promptly for query and resolution.

7.2. Handling of Missing and Incomplete Data

Missing clinical outcome data can occur for multiple reasons, including missed subject visits and scales or measures with missing item scores. Missing and incomplete data will be identified through the data quality review plan for this study. Missing and incomplete data will be identified for investigation, and possible resolution, by Data Management prior to the study database lock or snapshot.

Unless specified otherwise, only the observed data (not imputed data) will be presented in listings.

7.2.1. Missing Medical History Related Dates

- If only day is missing, impute 1.
- If month is missing, impute January 1st.
- If year is missing, then no imputation will be done; the date will be missing.

If the imputed date is earlier than the birth date, then the birth date will be used.

7.2.2. Missing Date Imputation for Adverse Events and Concomitant Medications

The following conventions will be used to impute missing portions of dates for adverse events and concomitant medications. Note that the imputed values outlined here may not always provide the most conservative date.

Missing Start Dates

- If the day is unknown, then:
 - If the month and year match the month and year of the DTX401 dose date, then impute the day of the DTX401 dose date.
 - Otherwise, assign the first day of the month.
- If the month is unknown, then:
 - If the year matches the year of the DTX401 dose date, then impute the month and day of the DTX401 dose date.
 - Otherwise, assign 'January'
- If the year is unknown, then the date will not be imputed and will be assigned a missing value.

Missing Stop Dates and not ongoing

- If the day is unknown, then assign the last day of the month.
- If the month is unknown, then assign 'December.'
- If the year is unknown, then the date will not be imputed and will be assigned a missing value, and the event will be considered ongoing. If the AE has been recorded as resolved/recovered, all efforts should be made to obtain the date from the Investigator.
- If the resulting end date is after the date of study completion / discontinuation / data cutoff, set the imputed end date as close to the date of study completion / discontinuation / data cutoff as possible without overwriting existing information.
- If the year is missing for the start date and stop date (observed or imputed) is on or after the DTX401 dose or event is ongoing, the start date will be imputed as the DTX401 dose date.

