7.2.3. Missing Causal Relationship to Investigational Product for Adverse Events

If the causal relationship to investigational product (DTX401) is missing for an AE that started on or after the date of the DTX401 dose, a causality of "related" will be assigned. The imputed values for causal relationship to DTX401 will be used for the incidence summary; the values will be shown as missing in the data listings.

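### SAP 7.2.2 imputes the dose date for partial start dates without reading the stop date, so a record that ended before dosing can start after it stopped; two bullets on an unknown start year also conflict

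*SAP*

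**What the plan says.** SAP 7.2.2 gives one rule set for two kinds of record: "The following conventions will be used to impute missing portions of dates for adverse events and concomitant medications".

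- **Start day unknown:** "If the month and year match the month and year of the DTX401 dose date, then impute the day of the DTX401 dose date". Otherwise the first of the month is used.
- **Start month unknown:** "If the year matches the year of the DTX401 dose date, then impute the month and day of the DTX401 dose date". Otherwise January is used.
- **Start year unknown, in the start-date list:** "If the year is unknown, then the date will not be imputed and will be assigned a missing value".
- **Start year unknown, at the end of the stop-date list:** a stop that does not precede dosing triggers dose-date imputation, and so does an ongoing record: "event is ongoing, the start date will be imputed as the DTX401 dose date".

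The classifications that use these dates are elsewhere in the SAP:

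- **SAP 5.3:** "Prior medication is defined as any medication started before the DTX401 dose date". A medication is concomitant if it ends on or after that date or is ongoing.
- **SAP 8.6.1:** a TEAE must occur on or after the dose and must not have been there before it, or must worsen afterwards.
- **SAP 7.2.3:** an AE with blank causality is set to related if it started on or after the dose date.

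**The concern.** The stop date is consulted only when the start year is missing, which is when least is known about the start. It is ignored when the day or month is missing, although a recorded stop before dosing would settle the question. The result can be an impossible record rather than merely an incautious one.

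Pre-dose records will exist. Protocol 9.1 collects AEs from consent, and the Protocol Synopsis allows a screening period of up to 56 days. TEAEs and related TEAEs belong to the primary endpoint (SAP 4.1). Protocol 10.2.5 counts prior medications as background information.

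Imputing the dose date is a sensible cautious choice for an AE that may have begun after infusion. It has no such purpose for a medication. SAP 7.2.1 uses the earliest date for medical history, so a condition and its treatment with the same partial start date can get different starts.

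**Working it through.** No sample-size or error-rate figure is involved. The check applies the rules literally to test records.

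**Inputs.** Imputation rules from SAP 7.2.2, medication definitions from 5.3, TEAE definition from 8.6.1. The dose date of 20 Mar 2020 is an assumption for illustration. UN marks an unknown part.

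**Rule as written.** Start = dose date if (day unknown, and month and year match dosing) or (month unknown, and year matches dosing). Prior: start < dose date. Concomitant: stop ≥ dose date, or ongoing. TEAE onset part: start ≥ dose date.

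| Record | Start | Stop | Imputed start | Result |
|---|---|---|---|---|
| AE | UN-Mar-2020 | 5 Mar 2020 | 20 Mar 2020 | 15 days after its stop (20 − 5); onset part met |
| AE | UN-UN-2020 | 10 Feb 2020 | 20 Mar 2020 | after its stop; onset part met |
| AE | UN-Mar-2020 | 25 Mar 2020 | 20 Mar 2020 | onset part met, reasonably |
| Medication | UN-Mar-2020 | 5 Mar 2020 | 20 Mar 2020 | neither prior nor concomitant |
| Medication | UN-UN-2020 | ongoing | 20 Mar 2020 | concomitant only |
| Medication | year unknown | ongoing | 20 Mar 2020 or missing, by bullet | concomitant only |
| Medication | year unknown | 1 Feb 2020 | missing | neither, although the stop shows it was prior |
| Medication | UN-UN-2012 | ongoing | 1 Jan 2012 | prior and concomitant, correct |
| Medication | UN-Feb-2020 | ongoing | 1 Feb 2020 | prior and concomitant, correct |

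For the first two AEs, a blank causality would also be set to related under 7.2.3, because that rule reads the start date.

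**Unknown start year.** One bullet leaves the date missing; the other sets it to the dose date if the stop is on or after dosing or the event is ongoing. For an ongoing medication, neither produces a start before dosing, so the prior definition fails both ways.

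**Weight of one subject.** SAP 3.5 plans 12 subjects in 4 cohorts of 3, and 8.1 tabulates by cohort and overall. 1/3 = 33.3 points; 1/12 = 8.3 points. This applies only where the subject is not already counted in the row.

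**Same records with a stop-date condition and an earliest-compatible date otherwise.** The first AE starts on 1 Mar and the second on 1 Jan (or at consent, if later); neither meets the onset part. The third AE stays at 20 Mar and still meets it. The medication stopped on 5 Mar starts on 1 Mar and is prior.

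**The case against.** The strongest objection concerns the AEs. A reader might infer that the SAP turns pre-dose AEs into TEAEs. Its text does not go that far: 8.6.1 and Protocol 9.1.1.2 both also require that the event was absent before exposure, and an AE with a recorded pre-dose stop fails that unless it later worsens. This stands. What remains is a programming risk, because the SAP does not say how prior presence is derived when the start is imputed. The second condition does nothing for medications.

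Three further readings go too far:

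- **That long-standing medications generally leave the prior table.** Starts in a known earlier month or year are imputed before dosing and stay prior. The day-unknown rule reaches only medications recorded as starting in the dosing month.
- **That every ongoing medication with unknown start year is dated to the infusion day.** One of the two bullets leaves the date missing, and the wording of the other refers to an event, so its reach to medications is arguable.
- **That chronic medications will be reported as started on the day of gene transfer.** SAP 7.2 shows observed dates in listings unless otherwise specified. The 8.4.4 tables count subjects by drug and class, with no start date described. Ongoing drugs remain in the concomitant table.

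It is also fair that queries before database lock (SAP 7.2) may leave few partial dates, and that 7.2.2 itself warns that its dates are not always the cautious ones. Yet the rules exist for whatever partial dates remain, and a warning does not prevent a start later than its stop.

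**Conclusion.** The point holds for the missing stop-date check and for the conflicting unknown-year bullets. For medications the rules as written give a wrong result: a drug with a matching partial start and a pre-dose stop appears in neither table. For AEs the result is an impossible date and a possible false TEAE, conditional on onset being taken from the imputed date alone. A false related TEAE needs a blank causality as well.

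The actual effect cannot be computed, because no document gives the number of partial dates. The upper size per affected subject is 33.3 points in a cohort row and 8.3 points overall, in descriptive tables. No test or decision limit is shown to move. The change is worth making before the tables are run, but it does not threaten the study's conclusions on the evidence available.

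**What to change.** Add to SAP 7.2.2:

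> Dose-date imputation applies only if the stop date (observed or imputed) is on or after the dose date or the record is ongoing. Otherwise impute the earliest date compatible with the recorded parts (for AEs, not before consent). An imputed start may not be later than the stop date.

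Then reconcile the two unknown-year bullets. Limit the version that imputes the dose date to AEs. State that a medication with unknown start year is counted as prior, and also as concomitant if it is ongoing or stopped on or after dosing, except steroids started for a post-dose ALT elevation. Keep the dose date for AEs that are ongoing or end after dosing.

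Two simpler remedies would not work. Using the first of the month gives no date when the month is unknown. Calling every medication prior unless shown to be post-dose could label reactive prednisone begun after infusion as prior, and steroid use is what separates Cohorts 2 to 4.

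One case stays as a convention: an ongoing medication with an unknown day in the dosing month, or an unknown month in the dosing year, still takes the dose date and is concomitant only. Its recorded parts do not show on which side of dosing it began.

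The cost is a few sentences in the SAP and one change to the date-imputation program. No new data are needed.

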7.2.3. Missing Causal Relationship to Investigational Product for Adverse Events

If the causal relationship to investigational product (DTX401) is missing for an AE that started on or after the date of the DTX401 dose, a causality of "related" will be assigned. The imputed values for causal relationship to DTX401 will be used for the incidence summary; the values will be shown as missing in the data listings.

7.3. Testing/Validation Plan

Data will be reviewed by a cross functional team periodically and issues will be addressed by data management.

7.4. Software

The CRM model will be used to evaluate each dose for dose escalation using software Fixed and Adaptive Clinical Trial Simulator (FACTS™; Berry Consultants, Austin, Texas, United States) Version 6.0 or later. SAS® software (SAS® Institute, Inc., Cary, North Carolina, United States) version 9.4 or higher will be used to perform statistical analyses unless otherwise specified.

8. STATISTICAL METHODS OF ANALYSES

8.1. General Principles

Continuous variables will be summarized by number of subjects and mean, standard deviation (SD), standard error (SE), median, Q1, Q3, minimum, and maximum values. Categorical variables will be summarized by number and percentage of subjects. All summary tables will be presented by scheduled study visit and no analysis windows will be used, unless specified otherwise. All the summary tables will be presented by dosing cohort of DTX401 and overall, unless specified otherwise. The dosing cohorts are:

- Cohort 1: Dose 1 $(2.0 \times 10^{12} \,\text{GC/kg})$ with a reactive steroid regimen (prednisone starting dose of 40 mg/day)
- Cohort 2: Dose 2 $(6.0 \times 10^{12} \,\text{GC/kg})$ with a reactive steroid regimen (prednisone starting dose of 40 mg/day)
- Cohort 3: Dose 2 $(6.0 \times 10^{12} \,\text{GC/kg})$ with an optimized reactive steroid regimen (prednisone starting dose of 60 mg/day)
- Cohort 4: Dose 2 $(6.0 \times 10^{12} \text{ GC/kg})$ with a prophylactic steroid regimen

8.1.1. The Continual Reassessment Method

Neuenschwander's CRM (or nCRM) (Neuenschwander et al., 2008) will be used to make recommendations for the dose to be administered in each cohort using all evaluable subjects (i.e., subjects who remain in the study for at least 12 weeks after dosing or for whom a DLT is observed within 12 weeks of dosing). The DLT assessment for each subject is based on the definition in Section 5.4. The DLT evaluation window for each subject starts on the date of administration of DTX401 and continues for up to 12 weeks (84 days) thereafter, or until all Week 12 safety assessments have been completed, whichever occurs later. Results of CRM model will be presented as part of DMC data review.

The target toxicity rate is 0.25. The cohort size is 3 subjects. The dose levels studied are specified in Section 3.2. The first cohort will be treated at 2×10^{12} GC/kg. Subsequent cohorts will be treated at the lower of the current estimate of the MTD and the highest dose allowed by the escalation rule. The CRM model will evaluate subjects based on the dose administered regardless of the steroid approach used.

A logistic model will be used to model the dose-toxicity curve; further details are provided in Appendix 2.

The CRM model will recommend that the study is stopped once the MTD is determined the first time any of the following criteria are satisfied after a CRM model update:

- Six evaluable subjects have been treated at 1×10^{13} GC/kg and the current estimate of the MTD is $> 1 \times 10^{13}$ GC/kg
- Six evaluable subjects have been treated at the current estimate of the MTD
- The current estimate of the MTD is $<2 \times 10^{12}$ GC/kg (insufficient safety)

The study will stop when the maximum sample size of 12 subjects have been enrolled or at the Sponsor's discretion. If 12 subjects have been enrolled and the definition of having an MTD determined has not been reached, then the highest dose considered at or below the MTD will be considered the MTD.

Enrollment will be limited so that each dosing cohort includes no more than 3 subjects. The optimal biological dose (OBD) will be based on the MTD and an assessment of clinical benefit.

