
Statistical Methods:
	
Determination of the Maximum Tolerated and Optimal Biological Doses
 
The optimal biological dose (OBD) will be based on the MTD and an assessment of clinical benefit.
 
A CRM will be used for dose escalation to estimate the MTD of DTX401. The CRM uses the Bayesian method to model the probability of experiencing a DLT for each given dose in order to recommend the dose for the next cohort. The CRM will evaluate subjects based on the dose administered regardless of the steroid approach used (ie, reactive vs prophylactic). A DLT is defined as any AE/SAE <math>\geq</math> Grade 3 that is considered by the Investigator and/or Sponsor to be related to DTX401. The MTD is defined as the highest dose where the predicted probability of experiencing a DLT is less than or equal to the target toxicity rate. In this study, the target toxicity rate is 0.25.
 
Interim Analysis
 
An interim analysis will be conducted when a minimum of 12-week data are available for all subjects from at least 2 dosing cohorts. Additional interim analyses may be conducted at the Sponsor's discretion.
 
Safety Analyses
 
All statistical analyses of safety outcomes will be descriptive, with the exception of the CRM modelling. The incidence of AEs and TEAEs will be summarized for each dose by system organ class and preferred term. Additionally, TEAEs may be summarized for each dose by severity and relationship to study product, if applicable. SAEs will be presented for each dose by relationship to study product. Summary tables will present the total numbers of TEAEs as well as the number of subjects with TEAE incidence by system organ class and preferred term. Subjects experiencing an event more than once with varying severity will be counted only once in the maximum severity within each system organ class and preferred term. For incidence of relationship to study product, subjects will be counted only once in the category of the strongest relationship to study product within each system organ class/preferred term.
 
Other safety data, including vital sign measurements, complete and targeted physical examination findings, ECG results, documented symptomatic hypoglycemic events, clinical laboratory data, vector shedding, vector genome determination, measurement of neutralizing antibody titer to AAV8, measurement of AAV8 binding antibody IgG, assessment of any cell mediated immune responses to AAV8 and G6Pase, and measurement of antiG6Pase antibodies will be summarized.

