hepatitis and treated with corticosteroids if needed (Section 8.2.6.2), having an interval of more than 14 days between subjects in Cohorts 1 and 2 and more than 7 days between subjects in subsequent cohorts does not change either safety evaluations or the medical management of study subjects. To date, no related serious adverse events (SAEs) or DLTs have been reported for DTX401. Consistent with previous experience (Manno et al., 2006; Nathwani et al., 2011b; Nathwani et al., 2014), mild, transient, asymptomatic increases in liver aminotransferase levels have been observed following DTX401 administration that resolved with steroids (Derks et al., 2019; Weinstein et al., 2019).

Subject safety will be closely monitored throughout the study, including assessment of hypoglycemic events, frequent monitoring of liver enzymes, and inpatient observation following dosing and at multiple time points throughout the 52-week study duration.

For Cohorts 1 and 2, there was a minimum of 12 weeks (84 days) between dosing of the last subject in a dosing cohort and the first subject in the next dosing cohort. After all subjects in Cohorts 1 and 2 completed Week 12, the continual reassessment method (CRM) proposed a dose for the next cohort using the collected data from the previous cohort. The DMC met to review safety data (ie, AEs/SAEs, physical examination findings, vital sign measurements, electrocardiogram [ECG] results, and clinical laboratory assessments [including assessment of liver function]) and provide a recommendation for progressing to the next dosing level (Section 9.3). The CRM will be used for dose escalation to estimate the maximum tolerated dose (MTD) of DTX401 (Section 10.2.1).

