3.5. Sample Size Considerations

Simulations show that if all 3 doses are safe and no DLTs occur, the CRM will recommend dose escalation to 1×10^{13} GC/kg (genome copies measured by and the recruitment of 12 subjects. Based on safety and efficacy observations in Cohorts 1, 2, and 3 (3 subjects each) and a positive recommendation from the DMC, it was decided to enroll a fourth cohort of 3 subjects. The planned sample size of the study will therefore be 12 subjects including 4 cohorts.

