12. APPENDICES

APPENDIX 2. CONTINUAL REASSESSMENT METHOD DETAILS

The nominal doses used in the continual reassessment method, the x-hats, will be derived as:

$$\hat{x}_i = \log\left(\frac{d_i}{d_{ref}}\right)$$

Where $d_1 = 2$, $d_2 = 6$, $d_3 = 10$ and $d_{ref} = 6$. The d_i correspond to the amount of DTX401 administered at each dose level, in units of 10^{12} genome copies/kg.

A logistic model will be used to model the dose-toxicity curve. Let

$$Y_i = \left\{ egin{array}{ll} 0 & if & the ith subject does not experience a DLT \\ & 1 & otherwise \end{array}
ight.$$

Then

$$p(Y = 1 | \hat{x}_i, \alpha, \beta) = \frac{e^{\alpha + \beta \hat{x}_i}}{1 + e^{\alpha + \beta \hat{x}_i}}$$

[figure not shown]
The joint distribution of α and β is given by

[figure not shown]
$$\begin{pmatrix} \alpha \\ \log \beta \end{pmatrix} \sim N \begin{pmatrix} \mu_{\alpha} \\ \mu_{\beta} \end{pmatrix}, \begin{pmatrix} \sigma_{\alpha} \times \sigma_{\alpha} & \sigma_{\alpha} \times \sigma_{\beta} \times \rho \\ \sigma_{\alpha} \times \sigma_{\beta} \times \rho & \sigma_{\beta} \times \sigma_{\beta} \end{pmatrix}$$

[figure not shown]
Initial (prior) values μ_{α} = -2.3097, $\log \mu_{\beta}$ = -0.4323, σ_{α} = 1.6604, $\log \sigma_{\beta}$ = 0.0044 and ρ = -0.2405 are used based on simulations.

The estimate of the maximum tolerated dose will be the highest dose for which the full Bayes posterior estimate of $p(DLT|d_i)$ is strictly less than or equal to the target toxicity rate.

[figure not shown]
A dose is cleared if it is either 2×10^{12} genome copies/kg or if it is no more than 1 dose level higher than the highest dose at which at least 3 subjects have been treated.

[figure not shown]

[figure not shown]

[figure not shown]

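### The 12-subject fallback can name as the MTD a dose that no subject received: with 3/9/0 subjects at Doses 1/2/3 and no DLTs, the model estimate is the untested 1.0 × 10^13 GC/kg

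*SAP*

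**What the plan says.** SAP 8.1.1 and Protocol 10.2.1 give three criteria for an MTD having been determined. Criterion 1 needs six evaluable subjects at 1.0 × 10^13 GC/kg. Criterion 2 reads "Six evaluable subjects have been treated at the current estimate of the MTD". Criterion 3 covers an estimate below Dose 1. If 12 subjects are enrolled and none of these is met, "then the highest dose considered at or below the MTD will be considered the MTD".

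The estimator is in Appendix 2 of both documents: "The estimate of the maximum tolerated dose will be the highest dose for which the full Bayes posterior estimate of" the DLT probability is at or below the target, which is 0.25. The protocol synopsis (Statistical Methods) defines the MTD in the same way, as the "highest dose where the predicted probability of experiencing a DLT is less than or equal to the target toxicity rate". The only condition on dose eligibility printed in the appendices is the clearing rule: a dose is cleared if it is Dose 1, or "if it is no more than 1 dose level higher than the highest dose at which at least 3 subjects have been treated".

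SAP 3.2 lists Doses 1, 2 and 3 (2, 6 and 10 × 10^12 GC/kg) as doses the CRM evaluates, and SAP 8.1.1 points to that list as the levels studied. Protocol 3.1 and 10.2.1 say only that these doses may be evaluated or studied. Cohort 1 receives Dose 1, and Cohorts 2, 3 and 4 receive Dose 2. SAP 3.5 records that "it was decided to enroll a fourth cohort of 3 subjects", for a planned total of 12. The model pools subjects by dose, whatever the steroid regimen.

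**The concern.** Criteria 1 and 2 tie a positive MTD declaration to six evaluable subjects at the dose. The fallback has no such tie, and the clearing rule does not supply one: three subjects at Dose 2 are enough to clear Dose 3 with nobody treated there.

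The fallback is reasonable for a design that climbs to Dose 3, which is the path SAP 3.5 describes for a trial without DLTs. It was not adapted when Cohorts 3 and 4 stayed at Dose 2. A dose-finding study could then report as its MTD a dose that is purely an extrapolation from Doses 1 and 2. The MTD is one of the two stated inputs to the optimal biological dose (OBD).

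The no-DLT case is realistic. Protocol 1.3.1 states "To date, no related serious adverse events (SAEs) or DLTs have been reported for DTX401", and SAP 3.7 reports no safety concerns from the DMC. Neither is a final DLT count.

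**Working it through.** **Inputs (Appendix 2 of both documents).** Logistic model: logit P(DLT) = α + β·log(d/6), with d = 2, 6, 10. The pair (α, log β) is bivariate normal, with α mean −2.3097, SD 1.6604, correlation −0.2405. The slope values are −0.4323 and 0.0044. They are labelled as logs of μ_β and σ_β, but the matrix uses μ_β and σ_β themselves as the mean and SD of log β. With exp(−0.4323) = 0.649 and exp(0.0044) = 1.004, four readings are possible:

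| Reading | Mean of log β | SD of log β |
|---|---|---|
| A | 0.649 | 1.004 |
| B | −0.4323 | 0.0044 |
| C | −0.4323 | 1.004 |
| D | 0.649 | 0.0044 |

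B and D make the slope almost fixed, so A and C are the more plausible. Posterior means were computed by integration on a grid.

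**The plan's own figure.** SAP 3.5 says that without DLTs the CRM escalates to Dose 3 and recruits 12. Applying the model, the clearing rule and the stop at six subjects to cohorts of 3 with no DLTs gives 3/3/6 under B, C and D, and 3/6/3 under A. All reach Dose 3 and N = 12, so the stated result is reproduced under every reading.

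**Planned allocation with no DLTs.** Posterior mean P(DLT) at Dose 3:

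| Data at Doses 1, 2 | A | B | C | D |
|---|---|---|---|---|
| 0/3, 0/3 (after Cohort 2) | 0.279 | 0.092 | 0.125 | 0.167 |
| 0/3, 0/6 (after Cohort 3) | 0.2495 | 0.072 | 0.103 | 0.131 |
| 0/3, 0/9 (after Cohort 4) | 0.231 | 0.060 | 0.090 | 0.110 |

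After Cohort 4 every value is at or below 0.25, so the estimate is Dose 3. Criterion 1 fails (0 subjects at Dose 3, not 6). Criterion 2 fails (0 at the current estimate, not 6). Criterion 3 does not apply. At the earlier updates criterion 2 also fails: after Cohort 2 only 3 subjects were at Dose 2, and after Cohort 3 the estimate is Dose 3. The fallback therefore operates with Dose 3 as the estimate.

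**Uncertainty.** The posterior probability that the Dose 3 rate exceeds 0.25 is 29%, 2%, 7% and 10% under A to D. At Dose 2, 0/9 has an exact two-sided 95% upper limit of 1 − 0.025^(1/9) = 33.6%. If one or two Dose 2 subjects are not evaluable, the Dose 3 mean is 0.063 to 0.237 (0/8) or 0.067 to 0.243 (0/7), and the estimate stays at Dose 3.

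**Effect of the prior label if DLTs occur.** Readings A and C, no DLT at Dose 1, all 12 evaluable. The last column restricts the declared MTD to treated doses and reports 'not determined' when the estimate is higher:

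| DLTs at Dose 2 | Dose 2 mean, A / C | Dose 3 mean, A / C | Declared, A / C |
|---|---|---|---|
| 1/9 | 0.107 / 0.101 | 0.336 / 0.171 | Dose 2 / not determined |
| 2/9 | 0.181 / 0.170 | 0.440 / 0.262 | Dose 2 / Dose 2 |
| 3/9 | 0.262 / 0.245 | both above 0.25 | Dose 1 / Dose 2 |

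**The case against.** **'Considered' may mean 'tried'.** On a model-only reading, the fallback says little more than that the MTD is the MTD. Reading 'considered' as 'actually used' gives the word a function and yields Dose 2. This is a fair reading, but neither document states it, and it sits badly with SAP 3.2 and 8.1.1, which list Dose 3 among the doses evaluated and studied. What stands is that the rule is ambiguous: it can name Dose 3, but need not.

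**The path under A is fragile.** The Cohort 3 value is 0.2495, only 0.0005 below the target. The posterior SD there is about 0.27. If the software samples the posterior, and assuming 10,000 independent draws, the Monte Carlo error is 0.27/√10,000 = 0.0027, about five times the margin. A value just above 0.25 would have met criterion 2 at Dose 2 with six evaluable subjects, and the fallback would never have applied. This stands as a caveat for A. B, C and D are far from the boundary.

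**The consequence is limited.** The MTD is neither an objective nor an endpoint, SAP 8.6.1 lists no MTD table, and the cohort labels show the dose given. The OBD also needs an assessment of clinical benefit, which cannot exist for a dose nobody received. A reader might infer that Dose 3 would be carried forward; the documents do not support that.

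**Figures are missing** around the clearing rule in the copy of both appendices reviewed. A further condition there cannot be excluded, although the running text of SAP 8.1.1 and Protocol 10.2.1 states the fallback without one.

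**Conclusion.** The point holds as a gap in a stated rule. With 3/9/0 subjects, all evaluable, and no DLTs, the model estimate is the untested 1.0 × 10^13 GC/kg under all four readings of the prior (posterior mean 0.060 to 0.231 against 0.25), and the text lets the fallback name it. The result rests on the no-DLT scenario, on 'considered' not meaning 'tried', and, under A, on the Cohort 3 value falling just below 0.25.

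Two stronger inferences are not supported. One is that the trial will report Dose 3 as its MTD: the documents give no final DLT count, and the wording allows Dose 2. The other is that limiting the MTD to treated doses makes the prior label harmless for up to two DLTs. At 1/9 the declared result still differs between A and C, and at 3/9 it differs again, so the label needs its own correction.

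This is a minor fix, given the limited role of the MTD.

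**What to change.** 1. In SAP 8.1.1 and Protocol 10.2.1, restrict the declared MTD to doses at which evaluable subjects were treated. If the model estimate exceeds the highest treated dose, report: MTD not determined; highest dose tested 6.0 × 10^12 GC/kg, with its DLT count. Record the change in SAP Section 9, which now lists none.
2. In Appendix 2 of both documents, replace the slope labels next to the values ("0.2405 are used based on simulations" closes that line) with the mean and SD of log β that were entered in the software.

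The cost is one sentence in two places, an entry in SAP Section 9 and a corrected label in two appendices. No subjects, visits or tables are added. If the fallback would have named Dose 3, the stated MTD conclusion becomes less favourable.
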